Once all samples are collected, chromatin will be extracted from the frozen PBMCs. Briefly, each vial containing 5×10^6 cells will be thawed and centrifuged at 300g for 5 min at 4°C . The supernatant will then be removed, and cells will be mixed with 100 μL of lysis buffer (10 mM NaCl, 3 mM MgCl₂, 10 mM Tris-HCl pH7.4, 0.1% Tween-20, 0.1% NP40) and lysed on ice for 4 min. Followed by 2x1ml washes (10 mM NaCl, 3 mM MgCl₂, 10 mM Tris-HCl pH7.4, 0.1% Tween20) before centrifuging at 500g for 5 min at 4°C .

Next, ATAC-seq libraries will be generated according to manufacturer guidelines. Briefly, transposition mix (Illumina, Cat# 20031198) will be added to the nuclear pellets, incubated at 37°C for 30 min, and DNA purified using the QIAGEN MinElute PCR Purification Kit (QIAGEN, Cat#28004). DNA fragments will be amplified by PCR for 10 to 11 cycles and resulting libraries purified using the QIAGEN MinElute PCR Purification Kit. The libraries will then be sequenced with an Illumina Novaseq 6000 S4 flow cell using 150 bp paired-end reads (Illumina, Cat# 20027466). FASTQ files will be generated from the NovaSeq BCL outputs and used as input to the ENCODE ATAC-seq pipeline (<https://github.com/ENCODE-DCC/atac-seq-pipeline>) using the MACS2 peak-caller with all default parameters. Differential accessibility will be initially calculated between groups using the csaw package.

To identify differentially open chromatin regions between groups from ATAC-seq, the R package edgeR will be used to fit a generalized linear model (GLM) to test for the effect of rehabilitation between T0 and T1 samples. In addition to time group (T0 vs. T1), we will also compare the two different rehabilitation treatments (cRHB vs. RAGT at T1). We will also use surrogate variable analysis (SVA) to capture unknown sources of variation (e.g., batch effects, age, sex, library preparation, etc) statistically independent from time or treatment group assignments. SVA decomposes the variation that is not accounted for by known factors such as time group or treatment into orthogonal vectors that can then be used as additional covariates when fitting a model to test for differential accessibility or expression.

Benjamini-Hochberg P value correction will be used to select differentially open peaks at an FDR of 5%.

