Differentially open ATAC-seq peaks will then be annotated with regard to functional and positional information. HOMER will be used to annotate peaks based on the relative gene position (promoter (± 2 kb of known TSS), intergenic,

intronic, among others). For functional annotation of peaks, we will use a simplified version of the 18-state ChromHMM-derived chromatin states (such as TSSs, enhancers, repressed polycomb, transcriptionally active, or other states such as ZNFs or heterochromatin) obtained from Roadmap Epigenomics data for PBMC and T cell subsets.

For gene-based analyses, HOMER will be used to assign each differentially open ATAC-seq peak to the nearest TSS, as measured from the peak center. We will then assess enrichment using the hypergeometric test followed by Benjamini-Hochberg FDR adjustment for P values, as previously mentioned.

Further functional and ontological enrichment analyses will be performed using ClueGO and WikiPathways that will allow us to identify pathways among genes associated to differentially open peaks.

Finally, we will scan the data for transcription factor (TF) footprints using the PIQ algorithm which integrates genome-wide TF motifs with chromatin accessibility estimates profiled at base pair resolution to generate a list of possible footprint matches for a motif. In a nutshell, this will allow the identification of chromatin accessibility blueprint generated by the different rehabilitation therapies tested in this trial, as well as gather valuable data of its underlying molecular mechanisms that in turn might lead to the identification of novel therapeutic targets.

Type outcome	Test	Baseline (T1)			RAG Session 1-24 (S1-S24)			end of training (T2)			Follow up at 2 months (T3)			Follow up at 1 year (T4)		
		CRO	PROMs	Blood sample	CRO	PROMs	Blood sample	CRO	PROMs	Blood sample	CRO	PROMs	Blood sample	CRO	PROMs	Blood sample
Pain	1	Pain registry		x			x			x			x			
Physiologic indicators	2	Heart rate	x			x			x			x				
	3	Arterial pressure	x			x			x			x				
Effort	4	Rating perception exertion The Borg R.P.E scale				x										
Fatigue:	5	Modified fatigue scale (MFIS)		x						x						
Depression	6	Hospital Anxiety and Depression Scale (HADS)		x						x						
Health-related quality of life	7	MSQoL 54 Health Survey		x						x						
Mobility	8	Modified Rivermead Mobility Index	x						x			x				
Disability	9	Expanded Disability Status Scale (EDSS) de Kurtzke	x						x			x				

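### The gene-level hypergeometric enrichment test ignores how many peaks each gene has, so gene sets rich in peaks can be called enriched without any set-specific effect

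*Combined protocol and SAP*

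**What the plan says.** Everything relevant is in Section 3.4 Assessments, under Molecular analysis.

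- **Peak selection.** "Benjamini-Hochberg P value correction will be used to select differentially open peaks at an FDR of 5" per cent. The peaks come from a before-after contrast, meant to "test for the effect of rehabilitation between T0 and T1 samples", and from a comparison of the two arms after training.
- **Peaks to genes.** Under the words "For gene-based analyses", the plan states: "HOMER will be used to assign each differentially open ATAC-seq peak to the nearest TSS, as measured from the peak center". It gives no distance limit and no weight for the number of peaks a gene has.
- **Test.** "We will then assess enrichment using the hypergeometric test followed by Benjamini-Hochberg FDR adjustment for P values". This sentence names neither the gene sets to be tested nor the background.
- **Pathways.** "Further functional and ontological enrichment analyses will be performed using ClueGO and WikiPathways", in order to "identify pathways among genes associated to differentially open peaks". This step names neither a test nor a background, but it works on the same genes.

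No peak-level test, permutation or peaks-per-gene correction appears in this section or in Section 4.

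**The concern.** The unit that is tested for differential accessibility is the peak, while the unit tested for enrichment is the gene. A gene is listed if any one of its assigned peaks is selected, so a gene with ten peaks has about ten times the chance of a gene with one when few peaks are selected. The hypergeometric model takes these chances as equal. A gene set whose members carry more peaks than average will then hold more listed genes than the model expects, even when the selected peaks have nothing to do with that set.

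Two steps in the plan might seem to protect against this, but do not. Benjamini-Hochberg controls multiplicity among valid p-values and cannot restore p-values that are too small. Surrogate variable analysis adjusts accessibility at each peak and does nothing about the number of peaks per gene.

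At stake are the secondary aims in Section 2.2 that concern genome regions, pathways and the molecular mechanisms of rehabilitation. A set could be reported as a mechanism because of its number of peaks.

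**Working it through.** The plan states no figure for this step, so there is none to reproduce. The inputs below are assumptions, except for the selection rule, the test and the Benjamini-Hochberg steps, which come from Section 3.4.

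**1. Mechanism, by hand.** Assume 20,000 genes with a mean of 5 peaks each, so P = 100,000 peaks. Let D peaks be selected without regard to any gene set. A gene with k peaks is listed with probability of about 1 - (1 - D/P)^k. For a set of 150 genes with D = 2,000 (D/P = 0.02):

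| Peaks per gene | Chance of listing | Expected listed genes of 150 |
|---|---|---|
| 5 (usual) | 1 - 0.98^5 = 9.6% | 14.4 |
| 7.5 (1.5 times) | 1 - 0.98^7.5 = 14.1% | 21.1 |
| 10 (2 times) | 1 - 0.98^10 = 18.3% | 27.4 |
| 15 (3 times) | 1 - 0.98^15 = 26.1% | 39.2 |

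The hypergeometric test expects about 14.4 listed genes in every row.

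**2. One set, before multiplicity adjustment.** Simulation with one set of 100 genes, every gene outside it having 5 peaks, 2,000 runs per setting, and rejection at p <= 0.05:

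| Peak excess in the set | 200 peaks | 1,000 peaks | 5,000 peaks |
|---|---|---|---|
| None | 1.6% | 2.5% | 3.3% |
| 1.6 times | 7.6% | 25.8% | 75.8% |
| 2 times | 13.8% | 49.5% | 97.8% |
| 3 times | 33.4% | 89.5% | 100% |

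A peak-level hypergeometric test, with all tested peaks as background, stayed between 1.6% and 5.4% in every setting, including settings where peaks per gene varied. Limiting the background to genes with at least one peak did not cure the bias. With variable peaks per gene and about 2 times the peaks, the rates were still 11%, 52% and 99%.

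**3. With the Benjamini-Hochberg step that the plan specifies.** Assume 300 sets of 150 genes, of which 1 or 15 are peak-rich, a background of genes with at least one peak, 300 runs, and the 5% level carried over from the peak step. The chance that a given peak-rich set is called, unadjusted and then adjusted:

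| Peak excess | 500 peaks | 2,000 peaks |
|---|---|---|
| 1.5 times | 16-17%, then 0.3% | 31-42%, then 1-3% |
| 2 times | 33-43%, then 2-3% | 69-80%, then 17-19% |
| 3 times | 66-83%, then 13-19% | 83-90% after adjustment |

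With 15 peak-rich sets, the chance of at least one call was 8-13%, 22-82% and 83-100% for the three rows. A second run of this set-up gave 0-3%, 2-23% and 15-92% for a given set, and 3-19%, 24-89% and 79-100% for at least one call. The two runs tell the same story, and the second is used in the conclusion.

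Because no set has a specific effect here, every call is false. The false discovery rate therefore equals the chance of at least one call, which is the quantity to compare with 5%.

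**4. Complete null.** Benjamini-Hochberg at 5% was applied to 100,000 independent null peaks in 2,000 runs. It selected any peak in 96 runs (96/2,000 = 4.8%), and in 88 of those it selected a single peak.

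**The case against.** The strongest reply concerns the null. A reader might infer that the plan would report pathways even if rehabilitation changed nothing. The documents do not support that. Peaks must first pass the 5% FDR threshold, and step 4 shows that with no true difference there is usually no gene list to test (independent peaks assumed; correlated peaks could give longer lists when any are selected). What remains is the case where a list exists but is unrelated to the gene set. That is plausible: a diffuse effect of training would produce such a list. So would any change over time in the before-after contrast, which has no untreated comparison. Surrogate variable analysis, as described, targets variation independent of time and treatment, so it would not remove such a change.

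A second reply is that unadjusted rates overstate what would be reported. This stands. At 1.5 times the peaks, adjustment brings a given set from 16-42% down to 3% or less, so the conclusion uses adjusted figures.

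Third, a reader might infer that immune pathways in particular would appear falsely in both contrasts. The documents give no peaks per gene, no set sizes and no expected number of differential peaks for either contrast. Whether immune pathways are peak-rich in these cells is an assumption.

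Fourth, the hypergeometric sentence does not mention pathways, and the ClueGO and WikiPathways step names no test. The point extends to that step only if its test also treats genes as equally likely.

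Finally, this is a secondary, hypothesis-generating analysis that can be corrected in code after the samples are collected. That limits the priority but does not remove the flaw.

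**Conclusion.** The concern holds in a limited form. The stated test assumes equal chances of selection, which the plan's own route from peaks to genes breaks, and no correction is stated. When a non-empty list of differential peaks exists, peak-rich gene sets can be called enriched with no set-specific effect.

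Under the assumptions in step 3, a given peak-rich set is called after adjustment about 0-3% of the time at 1.5 times the usual peaks, 2-23% at 2 times and 15-92% at 3 times. With 15 such sets, at least one false call occurs about 3-19%, 24-89% and 79-100% of the time. The problem is therefore minor for a modest peak excess and serious for a large excess with a long peak list. Which of these applies can be checked only in the trial's own peak set. The primary comparison on the 10-MWT is not affected.

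**What to change.** In the gene-based paragraph of Section 3.4, name the gene sets and the background, and replace the plain gene-level test with one of these:

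- an enrichment test at peak level, with all tested peaks as the background; or
- a gene-level test weighted by the number of tested peaks per gene (Wallenius non-central hypergeometric).

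For the lists sent to ClueGO and WikiPathways, state the test used and apply the same correction, or compare the results with those from matched random peak sets. Tabulate tested peaks per gene for each reported set, so that a reader can see whether it is peak-rich.

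The cost is analysis code only, with no new samples or assays. The downside is that fewer pathways will be reported as significant. The choice should be written down before the sequencing data are analysed.

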3.4.2 Schedule

Following completion of day 1 assessments and randomization, all subjects will be scheduled for the intervention phase of the study. Each participant will receive 24 sessions of RAGT or cRHB scheduled for three times a week for 8 weeks. If a subject cancels a treatment session, it will be counted as missed session. If a subject misses three consecutive treatment sessions, they will be dropped from the study due to inconsistency in treatment carryover. Cancellations and changes in patient scheduling represent a true clinical environment and represents normal clinical patient management.

At the end of the intervention phase, a new exploration will be carried out.

[figure not shown]

Figure 1 schedule

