comes in a clinically meaningful way in PwMS, RAGT seems more effective compared to conventional rehabilitation, while it shows similar effects if compared to specific balance and gait training in studies with level 2 evidence.¹¹ RAGT has several advantages in terms of patient motor assistance, intensity of training, safety, and the possibility to combine other therapeutic approaches and should be promoted for PwMS with severe disability in a multimodal rehabilitation context as an opportunity to maximize recovery.¹¹ In this context is needed a further larger-scale, better-designed RCTs with a longer training duration and more studies evaluating the satisfaction, usability and effectivity of RAGT.^{10 12 13 11}

The Atalante exoskeleton is composed of an external, powered, motorized orthosis that is placed over a person's limbs to provide self-ambulation functions without the use of crutches or other technical aids. The main feature of the exoskeleton is that it is fully actuated with 12 actuated degrees of freedom: three at each hip, one at each knee, and two at each ankle.^{14 15}

The molecular bases associated with the functional improvements derived from rehabilitation therapies or physical exercise are not yet well defined. However, both rehabilitation and exercise have been recognized for their immunomodulatory properties. In fact, recent clinical and preclinical findings have established a connection between physical activity and rehabilitative interventions with discernible epigenetic alterations in immune cells. For example, recent preclinical research has demonstrated how moderate-intensity training induces lasting changes in chromatin accessibility in macrophages, resulting in moderation of their inflammatory responses. However, there is still a lack of comprehensive epigenomic studies examining the repercussions of rehabilitation therapies in individuals with multiple sclerosis.

2 Aims

2.1 Primary Aim:

- To compare the effect of RAGT by use of Atalante self-balance exoskeleton with conventional rehabilitation training (cRHB) for improving **Walking speed** measured by the Timed 10-meters walk test (10-MWT), considering a clinically relevant change an improvement of 20% of the velocity (m/s) with respect to the baseline assessment.¹⁶

2.2 Secondary Aims:

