- To compare the effect of RAGT by use of the Atalante self-balance exoskeleton with conventional Rehabilitation training (cRHB), for improving **static balance**, **dynamic balance**, mobility, and **self-perception of gait impairment** measured with:
 - **Static Balance** by the Berg Balance Scale (BBS), considering a clinically relevant change for improvement in balance as measured by BBS was +3 points, meaning that PwMS are likely to perceive that as a reproducible and clinically important change in them balance performance.¹⁷
 - **Dynamic balance** by the Timed Up and Go test (TUG)¹⁸
 - **Mobility** measured by modified Rivermead Mobility Index (mRMI)¹⁹

- **Self-perception of gait** impairment by Multiple Sclerosis Walking Scale-12 (MSWS-12)²⁰
- **Instrumented gait analysis** by the G-walk device (assessing gait cycle duration, step length, propulsion index, support phase percentage D/I, oscillation phase percentage D/I, double/unique support phase percentage).
- To compare the effect of RAGT by use of the Atalante self-balance exoskeleton with conventional Rehabilitation training (cRHB) on quality of life, emotional status and fatigue measured at pre and post-intervention with:
 - Multiple Sclerosis Quality of Life-54 (MSQoL 54 Health Survey Spanish version)²¹
 - Hospital Anxiety and Depression Scale (HADs) considering a clinically relevant change of 1.7 points at HADs²²
 - The Modified fatigue scale (MFIS) ^{23 24}
 - The patient' physical effort of each session by means of the scale of perception of the effort R.P.E of Borg at the end of each training^{25 26}.
 - To evaluate the epigenetic blueprint of rehabilitation training by comparing the genome wide chromatin accessibility of peripheral blood mononuclear cells (PBMCs) before and after RAGT or cRHB, by Assay for Transposase-Accessible Chromatin sequencing (ATACseq).
 - To test the hypothesis that genome wide chromatin accessibility compared to clinical measures can be useful for identifying molecular mechanisms underlying rehabilitation therapies.
 - To compare the changes induced by RAGT versus cRHB on the overall chromatin accessibility, and specific genome regions and pathways.
 - Use the biological samples to provide additional functional and mechanistic information about the rehabilitation effects and subject health, disease or state.

3 Materials And methods

3.1 Design:

This trial is a prospective, randomized, rater-blinded study (cRHB (N=30) vs RAGT (N=30)).

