3.2.1 Inclusion criteria

- Male or female, between 18 and 75 years of age.
- Confirmed diagnosis of MS.
- EDSS from 6.0 to 7.0.
- Able to maintain the upright position on a daily basis.
- Stable course of disease-modifying therapy over the past 6 months.
- Clinical comorbidity asymptomatic (i.e., no underlying cardiovascular disease)
- Height: between approximately 1.50 m. and 1.90 m.
- Willingness to visit the Multiple Sclerosis Center of Catalonia (Cemcat) for testing and training.
- Gait disorder conditioned by paresis or hemiparesis associated with ataxia or sensory problems.
- Patient having given written consent.
Atalante is able to accommodate the following limb lengths:
- Thigh: 380-460mm.
- Distance between the ground and the joint space of the knee (to be measured while wearing the shoes they intend to wear with Atalante):
 - 457–607mm for patient with an ankle dorsiflexion $\geq 16^\circ$
 - 457–577mm for patient with an ankle dorsiflexion between 13° et 16°
 - 457–567mm for patient with an ankle dorsiflexion between 10° et 13°
 - 457–557mm for patient with an ankle dorsiflexion between 0° and 10°
- Hip with less or equal to 460mm when seated.
- Maximum weight: 90 kg.

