3.4 Assessments

The following information will be collected for all patients: age, sex, weight, height, type of MS, years from the diagnosis, Expanded Disability Status Scale (EDSS) and type of support device.

To ensure that training sessions are well tolerated, we will assess patients' blood pressure and heart rate weekly. We will also monitor the appearance of pain in any part of the body related to the RAGT at end of each training session using a pain registry (type of pain, location, intensity)²⁷.

3.4.1.1 To reduce the incidence of any type of muscle injury the physical therapist before each RAGT session will assess the level of spasticity using the Numeric Rating Scale measure of spasticity (NRS). The 0–10 NRS asks patients to indicate their level of spasticity on a scale of 0–10, where 0 is no spasticity and 10 is the worst possible spasticity. This type of rating tool is widely utilized in clinical settings to quickly assess pain.²⁸

A record of any unexpected Serious Adverse Events (SAE) within trial episodes will be kept. These are defined as death, a life-threatening adverse event or an event occurring as a result of the use of the device that requires medical intervention.

After the 8 weeks of rehabilitation treatment (T2) and, if possible, one year after T4, peripheral blood (6ml) will be taken from all subjects to perform the subsequent molecular analysis.

Molecular analysis

Peripheral blood mononuclear cells (PBMCs) will be purified using the Ficoll-Hypaque density gradient method according to manufacturer's instructions. Briefly, whole blood will be extracted by venepuncture and collected in CPT Vacutainer tubes (Becton Dickinson, BDAM362781) and centrifuged at 2250g for 25 min. Supernatant will then be collected, and washed twice with enriched saline (0.9% NaCl, 2%FBS). PMBC containing pellet will then be resuspended with 1 ml of complete media (RPMI1640 + 2% FBS) and cells will be counted and assessed for viability using a Countess 3 automated cell counter (Invitrogen). PBMCs will be adjusted to 5×10^6 cells/ml in freezing media media (90% FBS, 10% DMSO), and frozen at -80°C using a [name]™ Freezing Container (Thermo Scientific™) for 24 h and stored in liquid nitrogen vapor phase.

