Descriptive statistics (i.e., mean, standard deviation) will be calculated for quantitative data (demographics and clinical characteristics and outcome measures). Frequencies will be calculated for qualitative variables. For the proportions, binomial proportion confidences will be calculated using the Wilson formulae. Proportions will be compared using the Newcombe formulae

The Wilcoxon bilateral matched-pairs test will be used to compare repeated measurement on a single sample (mean, standard deviation).

Study data were collected and managed using REDCap electronic data capture tools hosted at the Mayo Clinic. REDCap (Research Electronic Data Capture) is a secure, web-based application designed to data capture for research studies, providing: 1) an intuitive interface for validated data entry; 2) audit trails for tracking data manipulation and export procedures; 3) automated export procedures for seamless data downloads to common statistical packages; and 4) procedures for importing data from external sources (Harris et al., 2009).

5 References

6. Larocca NG. Impact of Walking Impairment in Multiple Sclerosis Perspectives of Patients and Care Partners Conclusions: Difficulty walking is a common impairment in people with MS, with adverse effects on the QOL of people with MS and care partners of a person with MS. *Patient.* 2011;4(3):189-201.

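### No allocation method or stratification factor is given and the only between-arm clinical method is unadjusted, so a chance imbalance in baseline walking severity would be neither prevented nor corrected

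*Combined protocol and SAP*

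**What the plan says.** Section 3.1 describes the design in one line: "This trial is a prospective, randomized, rater-blinded study (cRHB (N=30) vs RAGT (N=30". Section 3.4.2 adds only "Following completion of day 1 assessments and randomization, all subjects will be scheduled for the intervention phase of the study". Neither section, nor any other readable text, mentions how the sequence is generated, whether it is blocked or stratified, or how it is concealed. Figure 1 (schedule) is not shown and is not held against the plan.

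The population is set by disability: "EDSS from 6.0 to 7.0" (section 3.2.1). Section 3.4 collects "Expanded Disability Status Scale (EDSS) and type of support device" for every patient, and Table 1 places EDSS and the 10-MWT at baseline (T1).

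The primary aim (section 2.1) compares the arms on 10-MWT walking speed, "considering a clinically relevant change an improvement of 20% of the velocity (m/s) with respect to the baseline assessment".

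Section 4 lists descriptive statistics, Wilson intervals for proportions, and two tests. The first is between arms: "Proportions will be compared using the Newcombe formulae". The second is within one sample: "The Wilcoxon bilateral matched-pairs test will be used to compare repeated measurement on a single sample". Neither uses a baseline covariate. The only adjustment in the document is in the molecular analysis, where "We will also use surrogate variable analysis (SVA) to capture unknown sources of variation" applies to the ATAC-seq data.

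**The concern.** The responder criterion is a percentage of the patient's own starting speed, so the chance of meeting it plausibly depends on how fast the patient walks at entry. A given absolute gain is a larger percentage for a slow walker than for a faster one, while more disabled patients may have less capacity to gain. The direction is open, but some dependence on baseline severity is likely.

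With 30 patients per arm, unstratified allocation can leave one arm with visibly more of the most disabled patients. An unadjusted difference in proportions carries that imbalance straight into the result. A positive or a null finding could then be disputed on baseline severity, with no pre-specified analysis to answer the challenge. An adjustment chosen after the baseline table has been seen would be less convincing than one written down now.

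**Working it through.** The plan gives no figure for imbalance or for response by severity, so there is none to reproduce. The sample-size statement in section 4 is a separate matter and is not used here.

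**Inputs from the documents:** 60 patients, 30 per arm (section 3.1); EDSS 6.0 to 7.0 (section 3.2.1); responder threshold of 20% (section 2.1); unadjusted Newcombe comparison (section 4).

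**Assumed inputs (not in the documents):** unstratified allocation with a fixed 30:30 split; K = 12, 18 or 24 patients at EDSS 7.0; response of 50% or 60% at EDSS 6.0 to 6.5 and 20% at EDSS 7.0, a gap d of 0.30 or 0.40. Reversing the sign of d reverses the shift and leaves its size unchanged.

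**Step 1: how often the arms differ.** If X of the K patients fall in one arm, X is hypergeometric (60, K, 30) and the arms differ by |2X − K|.

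| K | P(difference ≥ 4) | P(difference ≥ 6) |
|---|---|---|
| 12 | 0.333 | 0.104 |
| 18 | 0.399 | 0.158 |
| 24 | 0.430 | 0.187 |

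**Step 2: the shift in the responder difference.** Shift = (difference in patients / 30) × d. For a difference of 6:
- 6/30 × 0.30 = 0.06
- 6/30 × 0.40 = 0.08

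**Step 3: the shift against sampling error.** With f = K/60, the mean response is p = (rate at EDSS 6.0 to 6.5) − f·d, and SE = √[2p(1 − p)/30].
- f = 0.3, d = 0.30: p = 0.41, SE = √(2 × 0.41 × 0.59/30) = 0.127, ratio 0.06/0.127 = 0.47
- f = 0.3, d = 0.40: p = 0.48, SE = √(2 × 0.48 × 0.52/30) = 0.129, ratio 0.08/0.129 = 0.62

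Over all six combinations the SE is 12.5 to 12.9 points and the ratio 0.47 to 0.62.

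**Step 4: what adjustment could recover.** The share of responder variance explained by the severity group is f(1 − f)d²/[p(1 − p)].
- Lowest (f = 0.2, d = 0.30, p = 0.44): 0.16 × 0.09/0.2464 = 0.058
- Highest (f = 0.4, d = 0.40, p = 0.44): 0.24 × 0.16/0.2464 = 0.156

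The range is about 6% to 16%.

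**Step 5: error rates under no treatment effect.** These come from exact enumeration of the 95% Newcombe interval with the same response rates.
- Given a difference of 6 patients, the chance that the interval falsely favours the less severe arm is 5.8% to 8.1% over the six combinations. It is about 2% when the arms are balanced.
- Averaged over all 30:30 randomisations, the two-sided error is 4.8% to 5.2%.

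**The case against.** The strongest reply is that chance imbalance is not bias. Randomisation protects the test over repeated allocations, and step 5 confirms it: the two-sided error stays at about 5%. The raised rates apply only after an imbalance has occurred, and a 6 to 8 point shift is less than one standard error. This stands, and it limits the point to precision and to the credibility of the single result.

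Three stronger readings are tempting, and the documents do not support them.
- **That the trial uses simple, unstratified randomisation.** The text does not say so. Blocked, stratified or minimised allocation would all fit it. The finding is that the method is unspecified, and the probabilities in step 1 hold only if allocation is in fact unstratified.
- **That the responder comparison is the declared primary test.** Section 2.1 names walking speed and a 20% threshold, but section 4 does not tie the Newcombe comparison to that aim or name any primary test. It is simply the only between-arm clinical method offered.
- **That patients at EDSS 7.0 respond less.** No response rate by EDSS is given. With a percentage-of-baseline criterion the relation could run the other way, or be small within a range of one EDSS point. If the gap is near zero, so is the shift.

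Stratification is also a choice rather than a requirement in a trial of 60 patients, and nothing in the documents supports a cut at EDSS 7.0. What remains is that the stated comparison ignores baseline values already collected, and that using them costs almost nothing.

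**Conclusion.** The point holds in a limited form: no safeguard against severity imbalance is written into either the allocation or the clinical analysis. If 12 to 24 patients are at EDSS 7.0 and allocation is unstratified, an imbalance of 6 or more such patients has a probability of 10% to 19%. With a 30 to 40 point response gap, a difference of 6 moves the responder difference by 6 to 8 points, against a standard error of about 13. The case mix, the gap and its direction are all assumptions. This does not invalidate the trial, but it is a cheap weakness to remove, and the unadjusted comparison should be replaced.

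**What to change.** **Analysis (section 4).** Pre-specify the between-arm comparison of patients reaching the 20% gain in 10-MWT speed as adjusted for baseline severity measured at T1. Two suitable forms are a stratum-weighted Newcombe difference by EDSS group, or a risk difference adjusted for baseline 10-MWT speed. The second addresses walking severity more directly, because baseline speed is the denominator of the outcome, and it needs no cut point. Choose one and keep the unadjusted difference as a supporting result.

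**Allocation (sections 3.1 and 3.4.2), if recruitment has not started.** State that allocation is 1:1 in permuted blocks of varying size within two strata of the same baseline factor, and is released only after the T1 data are entered. The sponsor should choose the cut point from the expected case mix. If recruitment is under way or complete, report the method actually used and rely on the adjusted analysis.

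**Cost.** Some protocol wording, a stratified list and slightly more analysis work. No new measurement is needed, and one two-level factor in 60 patients carries little risk of over-stratification.
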